7.3.12.3. Time to First Course of Systemic Steroids

A summary and graph of the Kaplan-Meier estimates of the cumulative proportion of participants with a first course of systemic steroids for nasal polyps over time will be provided.

7.3.13. Number of Courses of Antibiotics

A summary of the number of courses of antibiotics will be presented for each treatment arm. Courses of antibiotics which are separated by less than 7 days will be considered a

continuation of the same course. Data will be included in the summary regardless of the occurrence of events such as surgery or treatment discontinuation.

7.3.14. Time to first nasal surgery or course of systemic steroids

The time to first nasal surgery or course of systemic steroids for nasal polyps will be determined as the number of days from the date of first dose of study medication to the date of first nasal surgery or course of systemic steroids for nasal polyps (see Section 14.6.5). If a participant withdraws from the study before experiencing nasal surgery or having a course of systemic steroids for nasal polyps, the event time will be censored at the time of study withdrawal.

7.3.14.1. Summary Measure

The summary measure of treatment effect will be the hazard ratio, the ratio of hazards corresponding to treatment with mepolizumab compared with placebo. For this endpoint the hazard represents the probability of nasal surgery or course of systemic steroids for nasal polyps for a participant at a given point in time following first dose of interventional product, given the participant has not experienced either event prior to that time.

7.3.14.2. Population of Interest

The primary population of interest is the ITT population.

7.3.14.3. Strategy for Intercurrent (Post-Randomisation) Events

A treatment policy strategy will be used for the intercurrent event of premature discontinuation of interventional product, such that available event times will be included in the analysis regardless of whether the event occurred prior to discontinuation of randomised treatment.

7.3.14.4. Statistical Analyses / Methods

Endpoint / Variables					

 Time to first nasal surgery or course of systemic steroids for nasal polyps 					
Model Specification					

 Cox proportional hazards model with covariates as follows: 
 
 Fixed Categorical:	Treatment group, Region	
 
 Fixed Continuous:	Baseline total nasal polyps endoscopic score (centrally read data), Baseline nasal obstruction VAS, Log_e baseline blood eosinophil count, Number of previous surgeries (1, 2, >2; ordinal)	
 
 
 Participants with missing covariate information will be excluded from the analysis 		Fixed Categorical:	Treatment group, Region	Fixed Continuous:	Baseline total nasal polyps endoscopic score (centrally read data), Baseline nasal obstruction VAS, Log _e baseline blood eosinophil count, Number of previous surgeries (1, 2, >2; ordinal)
Fixed Categorical:	Treatment group, Region				
Fixed Continuous:	Baseline total nasal polyps endoscopic score (centrally read data), Baseline nasal obstruction VAS, Log _e baseline blood eosinophil count, Number of previous surgeries (1, 2, >2; ordinal)				
Model Checking & Diagnostics					

 A log(-log(survival)) plot by treatment group will be used to assess the assumption of proportional hazards. 					
Model Results Presentation					

 The number of participants with an event, the number censored due to study withdrawal and at study completion will be presented by treatment arm. The hazard ratio with corresponding 95% CI and p-value from the Cox proportional hazards model will be presented. A summary and graph of the Kaplan-Meier estimate of the cumulative proportion of participants with nasal surgery within each treatment arm over time will be produced. 					
Subgroup Analyses					

 No subgroup analyses are planned for this endpoint. 					
Sensitivity and Supportive Analyses					

 No sensitivity/supportive analyses are planned for this endpoint. 					

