### **9.1.3. Critical procedures performed at Screening (Visit 1)**

- Medical history including smoking status, history of sinusitis, NP history (including NP surgery), aspirin sensitivity, history of asthma, courses of rescue corticosteroids in the past 12 months, asthma exacerbation history in the previous 12 months, smoking history.
- Therapy/Concomitant medication history, including use of mepolizumab, omalizumab or previous biologics in the past 12 months.

- Cardiovascular medical history/risk factors (as detailed in the eCRF). This assessment must include a review of the participant responses to the cardiovascular assessment questions and height, weight, blood pressure, smoking history, medical conditions, and family history of premature cardiovascular disease.
- Physical exam
- Vital signs
- Dispensing and training of eDiary
- Nasal obstruction VAS symptom score
- Overall VAS symptom score
- Resting 12-lead ECG
- Laboratory tests. These should include:
  - Chemistry
  - Haematology with differential count
  - Hepatitis B Surface Antigen and hepatitis C antibody
  - Urinalysis
  - Urine pregnancy test- for all WOCBP
  - FSH will be assessed to confirm child-bearing status (if applicable)
  - Parasitic screening (only in countries with a high-risk or in participants who have visited a high-risk country)
- Endoscopic NP score
- Review of Inclusion/Exclusion criteria
- Review of exacerbations, SAEs

Procedures conducted as part of the participant's routine clinical management [e.g. blood eosinophil counts] and obtained prior to signing of informed consent may be utilised for screening or baseline purposes provided the procedure meets the protocol-defined criteria and has been performed within the timeframe defined in the SoA.

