5.4. Examination of Covariates, Other Strata and Subgroups

5.4.1. Covariates and Other Strata

Covariates to be included in the statistical analysis models of the co-primary efficacy endpoints:

- Randomised treatment group
- Region
- Baseline score
- Baseline \log_e blood eosinophil count

Covariates to be included in the statistical analysis model of time to first nasal surgery:

- Randomised treatment group
- Region
- Baseline total NP endoscopic score (based on centrally read data)
- Baseline nasal obstruction VAS
- Baseline \log_e blood eosinophil count
- Number of previous surgeries (1, 2, >2; as an ordinal variable)

Covariates to be included in the statistical analysis model of proportion of subjects with at least one course of systemic steroids for nasal polyps up to Week 52:

- Randomised treatment group
- Region
- Baseline total NP score (based on centrally read data)
- Baseline nasal obstruction VAS
- Baseline \log_e blood eosinophil count
- Number of OCS courses for NP in the previous 12 months (0, 1, >1, as an ordinal variable)

Section 7 provides full details of the analysis methods for each of the efficacy endpoints.

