7.2.4.4. Statistical Analyses / Methods

Endpoint / Variables					

 The proportion of subjects requiring at least one course of systemic steroids for nasal polyps up to Week 52 					
Model Specification					

 A logistic regression model will be used to compare the proportion of participants requiring a course of systemic steroids up to week 52 in the mepolizumab arm compared to placebo. The odds ratio comparing treatment groups will be estimated using the observed marginal distribution of the sample covariates. The analysis model will include the following terms: 
 
 Fixed Categorical:	Treatment group, Region	
 
 Fixed Continuous:	Number of OCS courses for NP in last 12 months (0, 1, >1; ordinal), baseline total endoscopic NP score (based on centrally read data), baseline nasal obstruction VAS score, Log_e baseline blood eosinophil	
 
 		Fixed Categorical:	Treatment group, Region	Fixed Continuous:	Number of OCS courses for NP in last 12 months (0, 1, >1; ordinal), baseline total endoscopic NP score (based on centrally read data), baseline nasal obstruction VAS score, Log _e baseline blood eosinophil
Fixed Categorical:	Treatment group, Region				
Fixed Continuous:	Number of OCS courses for NP in last 12 months (0, 1, >1; ordinal), baseline total endoscopic NP score (based on centrally read data), baseline nasal obstruction VAS score, Log _e baseline blood eosinophil				

 Participants with missing covariate information will be excluded from the analysis 					
Model Checking & Diagnostics					

 Models will be checked for issues with convergence 					
Model Results Presentation					

 The number and percentage of participants identified as requiring at least one course of systemic steroids for nasal polyps will be displayed by treatment group, as will the number of courses of therapy required. The estimated odds ratio, 95% CI and p-value comparing treatments from the logistic regression model will be displayed. 					
Subgroup Analyses					

 No subgroup analyses are planned for this endpoint. 					
Sensitivity and Supportive Analyses					

 No sensitivity/supportive analyses are planned for this endpoint. 					

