14.12.4. Study Population Tables

Study Population Tables					
No.	Population	IDSL / Example Shell	Title	Programming Notes	Deliverable [Priority]
Subject Disposition					
1.1.	ITT	SD1	Summary of Treatment Status and Reasons for Discontinuation of Study Treatment	ICH E3	SAC [1]
1.2.	ITT	SHELL	Summary of Time On- and Off-Treatment by Withdrawal Scenario	Withdrawal scenarios are detailed in Section 14.7.2.3. Add footnote to indicate exclusion of data from the follow-up period after Week 52	SAC [2]
1.3.	ITT	ES1	Summary of Subject Disposition (Week 52)	ICH E3, FDAAA, EudraCT	SAC [1]
1.4.	FU	ES1	Summary of Subject Disposition (Follow-Up Period after Week 52)		SAC [2]
1.5.	FU	SHELL	Summary of Duration of Time in Follow-Up Period after Week 52		SAC [2]
1.6.	ENROLLED	ES6	Summary of Screening and Run-In Status and Reasons for Screen and Run-In Failures	Journal Requirements	SAC [2]
1.7.	ENROLLED	NS1/SHELL	Summary of Number of Subjects by Region, Country and Centre	EudraCT/Clinical Operations Add in column for region, add a total for each region and a total for each country.	SAC [2]
Protocol Deviation					
1.8.	ITT	DV1	Summary of Important Protocol Deviations	ICH E3	SAC [2]
Population Analysed					
1.9.	ENROLLED	SP1	Summary of Study Populations	IDSL	SAC [1]
1.10.	Randomised	SP2A	Summary of Exclusions from the Intent-to-Treat and Safety Populations	IDSL	SAC [2]

CONFIDENTIAL

205687

Study Population Tables					
No.	Population	IDSL / Example Shell	Title	Programming Notes	Deliverable [Priority]
Demographic and Baseline Characteristics					
1.11.	ITT	DM1	Summary of Demographic Characteristics	ICH E3, FDAAA, EudraCT	SAC [1]
1.12.	ENROLLED	DM11	Summary of Age Ranges	EudraCT	SAC [2]
1.13.	ITT	DM5	Summary of Race and Racial Combinations	ICH E3, FDA, FDAAA, EudraCT	SAC [2]
1.14.	ITT	Shell	Summary of Nasal Polyps Disease History and Characteristics	Include Disease Duration (years/months); Number of previous surgeries; Number of Courses of OCS for NP in previous 12 months. Baseline Nasal Polyps endoscopy score (centrally read and investigator read); Baseline SNOT-22.	SAC [1]
1.15.	ITT	Shell	Summary of Previous Exacerbation History	To include separate summary of information for Asthma and COPD Exacerbation History	SAC [2]
Medical Conditions					
1.16.	ITT	MH4	Summary of Past Medical Conditions	ICH E3	SAC [2]
1.17.	ITT	MH4	Summary of Current Medical Conditions	ICH E3	SAC [2]
Prior and Concomitant Medications					

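### The Cox model for time to first surgery or steroid course omits prior OCS courses, although the SAP adjusts its steroid endpoint for them; adding the term is nearly free and helps power if it is prognostic

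*SAP*

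**What the plan says.** SAP 7.3.14.4 defines the endpoint as "Time to first nasal surgery or course of systemic steroids for nasal polyps". The Cox model contains treatment group, region, baseline endoscopic NP score, baseline nasal obstruction VAS, log baseline eosinophils and "Number of previous surgeries (1, 2, >2; ordinal"). There is no term for previous steroid courses.

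This list is identical to the one for the surgery-only model in SAP 5.4.1 and 7.2.1.4. For the secondary endpoint on systemic steroid use, SAP 5.4.1 lists "Number of OCS courses for NP in the previous 12 months (0, 1, >1, as an ordinal variable"), and the logistic model in 7.2.4.4 repeats it as "Number of OCS courses for NP in last 12 months (0, 1, >1; ordinal").

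The variable is available at baseline. Protocol 9.1.3 has sites record "courses of rescue corticosteroids in the past 12 months" at screening, the schedule of activities has a medication history item covering OCS use for polyps, and SAP Table 1.14 (14.12.4) summarises "Number of Courses of OCS for NP in previous 12 months".

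Two further statements in 7.3.14.4 matter here: "Participants with missing covariate information will be excluded from the analysis", and "No sensitivity/supportive analyses are planned for this endpoint".

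**The concern.** The SAP adjusts the surgery endpoint for surgical history and the steroid endpoint for steroid history. The composite counts whichever event comes first but adjusts only for surgical history. The SAP does not explain the difference.

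A Cox hazard ratio is non-collapsible. If a covariate is prognostic, the hazard ratio from a model without it lies closer to 1 than the hazard ratio conditional on it, even under perfect randomisation. The test keeps its size but can lose power. A hazard ratio, confidence interval and p-value will be reported for this endpoint (Table 2.55), and no sensitivity analysis would show how much the covariate choice matters.

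**Working it through.** **Is the omission a choice or a carry-over?** The covariates in 7.3.14.4 match 7.2.1.4 term for term. The results paragraph of 7.3.14.4 also promises a Kaplan-Meier estimate for participants with nasal surgery, which describes the surgery endpoint and not the composite. That suggests, without proving it, that the section was copied and not adapted.

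**The plan's own figure.** No power is stated for the composite. The nearest figure is Protocol 10.1: 200 per arm, surgery in 40% against 25%, two-sided 5%, 90% power.

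- Two proportions: [0.15 − 1.960 × √(2 × 0.325 × 0.675/200)] / √[(0.40 × 0.60 + 0.25 × 0.75)/200] = (0.15 − 0.0918)/0.0462 = 1.26, so power is 89.6%.
- Schoenfeld: the implied HR is ln(0.75)/ln(0.60) = 0.563 and the expected events are 200 × (0.40 + 0.25) = 130. Then (√130/2) × |ln 0.563| − 1.960 = 1.31, so power is 90.5%.

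Both agree with the protocol's 90%.

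**Effect of leaving the term out.** From the documents: 200 per arm, 1:1, 52 weeks, two-sided 5%, categories 0, 1, >1. Assumed, because the documents do not give them:

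- category mix 50/30/20 or 34/33/33
- placebo composite event rate and conditional HR of 40% with 0.563, 60% with 0.60, or 60% with 0.70
- prognostic HR per category from 1.0 to 3.0

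The hazard is λ·exp(γx + ln(HR)·treatment), with x = 0, 1, 2 and λ set to give the assumed placebo rate. There were 800 simulated trials per scenario, each fitted with and without x. Shrinkage is 1 − ln(HR omitted)/ln(HR adjusted). The ranges below run over the six combinations of mix, event rate and HR.

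| Prognostic HR per category | Implied HR, >1 vs 0 | Shrinkage of log HR | Power lost by omission (points) |
|---|---|---|---|
| 1.0 | 1.0 | 0.1-0.2% | −0.3 to 0.4 |
| 1.25 | 1.56 | 0.7-1.2% | −0.1 to 0.8 |
| 1.5 | 2.25 | 2.1-4.2% | 1.6 to 4.0 |
| 2.0 | 4.0 | 5.4-10.8% | 4.2 to 9.9 |
| 3.0 | 9.0 | 13.0-25.3% | 10.6 to 25.1 |

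The small negative values are simulation noise.

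Two examples at 2.0 per category, mix 50/30/20, placebo rate 60%:

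- Conditional HR 0.60: 0.636 omitted against 0.603 adjusted; power 90.1% against 95.2%; SE of log HR 0.141 in both.
- Conditional HR 0.70: 0.725 omitted against 0.699 adjusted; power 66.1% against 76.0%; SE 0.137 in both.

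Across all scenarios the ratio of adjusted to omitted SE is 1.001 to 1.010, so adjustment does not shrink the standard error. Any gain in power comes from the estimate moving away from 1.

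The simulation contains only treatment and the OCS term. The planned model already adjusts for NP score, obstruction VAS, eosinophils, previous surgeries and region. Overlap between these and prior OCS use would reduce what the extra term adds.

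**The case against.** The model is prespecified, uses the same covariates as the key secondary surgery model, and has the same list in the 2019 RAP reproduced with the SAP. One covariate set for both time-to-event models is defensible, although the SAP does not give that reason. The endpoint sits under Other Efficacy Analyses (7.3). It is absent from the objectives and endpoints tables and from the hierarchy in 5.5, and its table is second-priority output. All of this stands, and it limits the point to a minor improvement.

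A reader might infer more than the documents support:

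- **That the planned analysis loses precision.** It does not; the standard error is no larger without the term.
- **That the hazard ratio is biased, or known to be attenuated.** The documents give no prognostic strength for prior OCS use, and the SAP lists its covariates without calling any of them a strong predictor. The less-adjusted hazard ratio is a less conditional estimand. It is not confounded, because treatment is randomised.
- **That the change is entirely free.** It uses one degree of freedom, and the complete-case rule would drop anyone with missing OCS history.

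Consistency with the surgery model does not explain why a composite containing the steroid event should ignore the history the SAP uses for that event.

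**Conclusion.** The inconsistency is real and minor. The composite Cox model carries over the surgery covariates and leaves out a collected baseline variable that the SAP uses for the other half of the composite.

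If prior OCS use is prognostic given the other covariates, the cost is a hazard ratio somewhat closer to 1 and some power: close to nothing at 1.25 per category, and up to about 10 points at 2.0 with a conditional HR of 0.70. The larger losses at 3.0 per category need a nine-fold hazard between the extreme categories, and nothing in the documents points to that.

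Prognostic strength, category mix, composite event rate and conditional HR are all assumptions. The test is valid either way, and no primary or secondary conclusion depends on this analysis.

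**What to change.** Before unblinding, add "Number of OCS courses for NP in last 12 months (0, 1, >1; ordinal") to the covariates of the Cox model in SAP 7.3.14.4, coded as in 7.2.4.4. Fixing it then avoids a later choice between two models with the results in view.

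No new data or derivation is needed. The cost is one degree of freedom and, under the complete-case rule, the loss of any participant with missing OCS history. The same rule already excludes those participants from the secondary steroid model.

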7.4. Participants with Asthma

A subgroup analysis by concurrent asthma will be carried out for each of the following endpoints:

- Total endoscopic nasal polyps score (Centrally Read)
- Nasal obstruction VAS score
- Proportion of subjects requiring systemic steroids for nasal polyps up to Week 52

In addition, for participants with asthma the Asthma Control Questionnaire (ACQ-5) score and number of clinically significant asthma exacerbations will be summarised. These summaries will be based on a dataset where the intercurrent events of surgery/sinuplasty and treatment discontinuation have been handled as detailed in Section 7.1.4.

7.5. Maintenance of response

The following endpoints will be summarised for the subset of participants who entered the no-treatment 6-month follow up period after Week 52. All data reported by these participants for the duration of their time in the study will be included in these summaries, this will include data reported prior to entering the follow-up period (whether or not the subject had prematurely discontinued from interventional product during that time) and data reported after entering the follow-up period.

- Change from baseline in total endoscopic NP score (centrally read)
- Change from baseline in mean nasal obstruction VAS score
- Change from baseline in mean individual VAS symptom score for nasal discharge, mucus in throat, loss of smell and facial
- Change from baseline in mean overall VAS symptom score
- Proportion of subjects requiring systemic steroids for nasal polyps
- Number of mgs per year of prednisolone-equivalent OCS dose
- Change from baseline in SNOT-22 total score
- Time to first nasal surgery
- Time to first inclusion on waiting list for NP surgery

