
 
To further evaluate the efficacy of 100mg mepolizumab compared to placebo on systemic steroid use such as OCS and antibiotic use as part of SoC
 
	
 
Number of Courses of systemic steroid therapy up to Week 52.
 
Number of mgs per year of prednisolone-equivalent OCS dose up to Week 52.
 
Number of days on systemic steroid therapy up to Week 52.
 
Time to first course of OCS up to Week 52.
 
Number of courses of antibiotic up to Week 52.
 

 
To further evaluate the efficacy of 100mg mepolizumab compared placebo in the sub-group of participants with Asthma
 
	
In addition to endoscopic NP score, VAS symptoms score, medication and surgery, the following asthma related endpoints will be assessed:
 
 
Change from baseline in Asthma Control Questionnaire (ACQ - 5) score at Week 52.
 
Number of clinically significant asthma exacerbations defined as worsening of asthma requiring systemic corticosteroids (i.v. or oral steroid) for at least 3 days or a single IM CS dose and/or ED visit and/or hospitalisation for asthma up to Week 52.
 

 
To assess the maintenance of response after cessation of mepolizumab treatment compared to placebo
 
	
For all participants who enter post treatment follow-up period, the following will be assessed at Week 76:
 
 
Change from baseline in total endoscopic NP score.
 
Change from baseline in mean nasal obstruction VAS score.
 
Change from baseline in mean individual VAS symptom score for nasal discharge, mucus in throat, loss of smell, facial pain and overall VAS symptom score during the 4 weeks prior to Week 76.
 
Number of mgs per year of prednisolone-equivalent OCS dose.
 
Change from baseline in SNOT-22 total score.
 
Change from baseline in SF-36 Mental Component Summary (MCS), Physical Component Summary (PCS) and 8 summary scores.
 
Change from baseline in WPAI Questionnaire.
 
Time to first nasal surgery including off treatment period from randomization to Week 76.
 
Time to first inclusion on waiting list for NP surgery up to Week 76.
 

Objectives	Endpoints
Safety	

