## **5.3. Participant and Study Completion**

Final treatment visit: For all participants this will be Week 52 (Visit 15), 4 weeks after the last expected injection at Visit 14.

Final study visit: for up to the first 200 randomized participants this will be Week 76 (Visit 18) and for the remainder will be Week 52 (Visit 15).

The end of the whole study is defined as the date of the last visit of the last participant in the study or last scheduled procedure shown in the SoA for the last participant in the trial globally.

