## 7. TREATMENTS

Study treatment is defined as any investigational treatment(s), marketed product(s), placebo, or medical device(s) intended to be administered to a study participant according to the study protocol.

The currently marketed drug product, Nucala (mepolizumab), is supplied as a 100 mg single-dose vial containing a sterile, preservative-free, lyophilized powder for reconstitution and subcutaneous injection.

A liquid formulation of mepolizumab is under development which will be provided as pre-filled syringes in a safety syringe device for this study. The liquid formulation has a distinct advantage over the lyophilized product as it does not require reconstitution, and the devices (upon commercial registration) will simplify and facilitate administration. The liquid formulation in a safety syringe device must be administered by a health care professional in this study.

There will also be a matched safety syringe with placebo. Both active and placebo drug products are stored at 2-8°C condition, protected from light.

The study treatment consists of up to 18 visits with a maximal total treatment duration of the study of approximately 52 weeks and maximum study duration of approximately 82 weeks. Screened participants will enter a 4 week run in period, followed by up to 52 week treatment period. Up to the first 200 randomized participants will be further followed up for a drug free period of up to 28 weeks with no injections.

Participants who are successfully enrolled into the study will be randomized into one of two treatment groups, receiving a total of thirteen doses (one every four weeks):

- Group 1: 100 mg SC of mepolizumab on top of SoC which includes intranasal mometasone furoate (MF)
- Group 2: Placebo SC on top of SoC which includes intranasal MF

All participants will be provided and are required to take MF at the maximum prescribable dose according to local label, if available, or as per local SoC. This is usually 400 micrograms ( $\mu\text{g}$ ), 2 actuations (50  $\mu\text{g}$ /actuation) in each nostril twice daily. For participants that are intolerant to this dose, the lower dose of 200 $\mu\text{g}$  can be used (2 actuations (50  $\mu\text{g}$  /actuation) in each nostril once daily).

Study treatment completion is taken as Visit 15 which is Week 52 of the study for each individual participant.

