 - CCI [REDACTED]
- Composite of nasal obstruction, nasal discharge, mucus in the throat, loss of smell and facial pain
 - CCI [REDACTED]

Nasal Surgery (reported on the disease related events page of the eCRF)
Time to first nasal surgery

 Calculated as (Date of first nasal surgery – Date of first dose of study treatment) + 1 Analysis excluding data from the follow-up period after Week 52: For participants who withdraw from the study before Week 52 and before experiencing surgery, event times will be censored at the time of study withdrawal For participants who complete to Week 52 without experiencing surgery, event times will be censored at the time of the Week 52 visit. Analysis including data from the follow-up period after Week 52: For participants who withdraw from the follow-up period before completion and before experiencing surgery, event times will be censored at the time of study withdrawal. For participants who complete the follow-up period without experiencing surgery, event times will be censored at time of completion of follow-up.
Need for surgery

 Need for surgery at Week 52 is based on the overall VAS symptoms score and the endoscopic NP score (centrally read). Participants will be classified as having a need for surgery if they meet the following: 
 Overall VAS symptoms score >7 (Weeks 49-52) and total endoscopic NP score ≥5 (Week 52, centrally read) Participants who have undergone nasal polyps surgery at any time prior to the week 52 visit, or who have a missing endoscopic NP score (centrally read) at Week 52, or missing overall VAS symptom score (Weeks 49-52) will be identified for analysis as still having a need for surgery.
Rate of surgery

 The crude rate of surgery will be presented for each treatment arm, this will be calculated as: $\left(\frac{\text{Total number of nasal surgeries}}{\text{Total number of days in the study}} \right) * 365.25$

Systemic steroid use
Conversion of glucocorticoid dose to mgs of prednisolone equivalent OCS use

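### SAP 7.5 pools Weeks 0-52 with the drug-free Weeks 52-76 for the cumulative maintenance endpoints; as written, the steroid summaries cannot separate a kept effect from a lost one

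*SAP*

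**What the plan says.** Protocol section 4 sets the objective: "To assess the maintenance of response after cessation of mepolizumab treatment compared to placebo". Its endpoints at Week 76 include scores measured at visits or over the preceding four weeks, and also cumulative ones: mg per year of prednisolone-equivalent steroid, time to first waiting-list inclusion, and "Time to first nasal surgery including off treatment period from randomization to Week 76".

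SAP 7.5 (Amendment 1, whose table numbers are used throughout) restricts the summaries to participants who entered follow-up. It then widens the data window: "All data reported by these participants for the duration of their time in the study will be included in these summaries", and "this will include data reported prior to entering the follow-up period". Its list adds the proportion requiring systemic steroids.

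SAP 14.6.5 gives one clock for surgery: "Calculated as (Date of first nasal surgery – Date of first dose of study treatment) + 1". When follow-up data are used, only the censoring changes: "For participants who complete the follow-up period without experiencing surgery, event times will be censored at time of completion of follow-up". For mg per year, it divides cumulative milligrams by the days in a period that it does not define.

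The displays are:
- Table 2.66 and Figure 2.23: time to first surgery.
- Figure 2.24: time to first waiting-list inclusion.
- Table 2.67: number of steroid courses.
- Table 2.68: mg per year, under the same title as the Week 52 Table 2.52.

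None of their programming notes limits the data to the time after Week 52. The words on follow-up in the titles match the FU population of SAP section 4, which is a set of participants and not a time window.

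**The concern.** A maintenance question concerns what happens after stopping. If a summary runs from first dose to Week 76, 52 of its 76 weeks fall in the treatment period, and any difference built up there stays in the result. A steroid saving that ended when dosing ended would still appear at Week 76 as a smaller saving. A reader of Tables 2.67-2.68 could not tell this from a modest effect that lasted.

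The SAP handles the same period differently elsewhere. Section 8 summarises follow-up safety data separately, and 14.4.1.1 and 14.4.1.4 already define a phase after Week 52 for efficacy assessments and for medication start dates. Section 7.5 does not use that phase.

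At stake is the answer to a stated objective for steroid use, and to a lesser degree for surgery and waiting list.

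**Working it through.** **Inputs**
- Surgery by Week 52: 40% placebo, 25% mepolizumab (Protocol 10.1).
- Phase II six-month surgery rates: 20% and 9% (Protocol 10.1).
- Off-treatment window: Week 52 to Week 76, 24 weeks. From the last dose at Week 48 it is 28 weeks, which is the protocol's "a drug free period of up to 28 weeks with no injections".
- About 100 per arm, assuming the 1:1 allocation holds among the first 200.
- Steroid rates are not given, so they are assumed and shown as ranges.

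**Check on the plan's own figure.** For 40% vs 25% with 200 per arm at two-sided 5%:
- SE under the null = sqrt(2 × 0.325 × 0.675/200) = 0.0468.
- SE under the alternative = sqrt(0.40 × 0.60/200 + 0.25 × 0.75/200) = 0.0462.
- z = (0.15 − 1.96 × 0.0468)/0.0462 = 1.26, so power is 89.6%. With unpooled variance it is 90.1%. The stated 90% reproduces.

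**Steroid mg per year, or courses as a rate.** Let r be the on-treatment ratio of mepolizumab to placebo, with a constant placebo rate and a ratio of 1 after Week 52. The pooled ratio is (52r + 24)/76.
- r = 0.5: 50/76 = 0.66
- r = 0.6: 55.2/76 = 0.73
- r = 0.8: 65.6/76 = 0.86

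**Steroid proportion (at least one course).** Assume 20-60% on placebo by Week 52, an on-treatment hazard ratio of 0.5-0.8, and complete loss afterwards. The Week 76 gap is then 3 to 15 points and the risk ratio 0.69 to 0.93. For example, 40% on placebo with hazard ratio 0.6 gives 52.6% vs 41.9% at Week 76.

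**Surgery.** With constant hazards, the hazard ratio is ln 0.75/ln 0.60 = 0.563.
- Placebo at Week 76: 1 − 0.60^(76/52) = 52.6%.
- Mepolizumab, effect lost at Week 52: 1 − 0.75 × 0.60^(24/52) = 40.8%. The gap is 11.8 points.
- Mepolizumab, effect kept: 1 − 0.75^(76/52) = 34.3%. The gap is 18.3 points.
- The gap at Week 52 is 15.0 points, so it narrows if the effect is lost and widens if it is kept.
- SE of the Week 76 difference under loss: sqrt(0.526 × 0.474/100 + 0.408 × 0.592/100) = 7.0 points.
- To close the gap by Week 76, the off-treatment mepolizumab hazard would have to be about 1.95 times the placebo hazard.
- Phase II rates carried to 12 months give 1 − 0.80² = 36.0% and 1 − 0.91² = 17.2%. Complete loss then leaves 47.9% vs 32.6% at Week 76, a gap of 15.3 points.

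**What a clock restarted at Week 52 would give.** About 60 placebo and 75 mepolizumab participants would be surgery-free.
- Risk over 24 weeks: 1 − 0.60^(24/52) = 21.0% in both arms if the effect is lost; 21.0% vs 1 − 0.75^(24/52) = 12.4% if kept.
- Events if kept: 60 × 0.210 + 75 × 0.124 = 12.6 + 9.3, about 22. SE of the log hazard ratio is sqrt(1/12.6 + 1/9.3) = 0.43, so 0.56 has a 95% CI of about 0.24 to 1.3.
- If risk varies between participants (gamma frailty, variance 0.5 to 2, assumed), complete loss gives 18.0% vs 19.8%, up to 12.1% vs 17.3%. Mepolizumab then looks worse although its effect has only ended.

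**The case against.** The strongest reply has five parts.

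- **The surgery and waiting-list figures have a time axis.** Participants event-free at Week 52 supply every later step of the Kaplan-Meier curves. A reader might infer from SAP 7.5 that a complete loss of effect on surgery would go unseen. The documents do not support that: Figures 2.23-2.24 would show the gap narrowing instead of widening. With about 100 per arm the signal is weak, but it is displayed.
- **Later steroid use does count.** A reader might infer that anyone treated before Week 52 adds nothing afterwards. That is true only of a yes/no proportion. Table 2.67 counts courses and Table 2.68 adds milligrams. The fault there is averaging, not saturation.
- **The table layouts are not in the document.** These displays are marked as shells, which SAP 14.13 offers on request, and the period for mg per year is undefined. It therefore cannot be said that no output will isolate Weeks 52-76. It can be said that the text of 7.5 points to the whole study and no programming note says otherwise.
- **Restarting the clock is no clean remedy.** It selects on an outcome that differs by arm, rests on few events, and may mix residual drug effect with washout. Protocol 5.5 reports sustained effect after stopping and blood eosinophils returning to baseline after about three months, in Phase II at a higher dose. Counting from randomization avoids that selection and is the protocol's own surgery endpoint.
- **The stakes are limited.** These are descriptive endpoints in the lowest tier. Protocol 5.1 gives model validation as the reason for following 200 participants and mentions maintenance second.

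All five stand and limit the point. None removes the pooling of the steroid summaries, which SAP 7.5 states as a rule.

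**Conclusion.** The point holds, mainly for steroids. As SAP 7.5 is written, complete loss of effect after Week 52 would leave a pooled mg/year ratio of 0.66-0.86 (assumed on-treatment ratio 0.5-0.8, constant placebo rate), with nothing described that separates the two periods. For surgery, the cumulative Week 76 figure would still favour mepolizumab by about 12 points after complete loss (planning rates, constant hazards, abrupt loss at Week 52). The planned curves show the course after Week 52, but no off-treatment estimate is described. The same reasoning applies to the waiting list, for which the documents give no rates.

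The split at Week 52 is approximate: the last dose is at Week 48, and data after early discontinuation are included. Type I error and the primary and secondary conclusions are unaffected. This is a worthwhile, low-cost correction to a descriptive analysis.

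**What to change.** 1. In SAP 7.5 and Tables 2.67-2.68, report the proportion with a steroid course, the number of courses and mg per year in two panels: Weeks 0-52, and the Week 52 visit to Week 76. Include all FU participants in both. In SAP 14.6.5, define the period for the second panel as follow-up days. Give Table 2.68 a title that distinguishes it from Table 2.52.
2. Keep the randomization-to-Week-76 displays for surgery and waiting list. Add, by arm, the number at risk at Week 52 and the number with a first event in Weeks 52-76, labelled descriptive.
3. If a hazard ratio from Week 52 is wanted, label it exploratory. State that it conditions on being event-free at Week 52, with selection that differs by arm; that it rests on few events (about 22 if the effect is fully kept); and that early follow-up may include residual drug effect.

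The cost is a few lines of SAP text and re-cut tables from data already collected, using the follow-up phase that SAP 14.4.1 already defines. The trade-off is wider uncertainty in a 24-week window.
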